5.3.2.2 UCVA

The mean UCVA at 3 months (Month 3) will be analyzed on eye level for the ITT Analysis Set using the statistic of Donner, et al (Donner 1981), which accounts for the intraclass correlation between eyes within subjects, based on the two-sided 5% significance level ($\alpha=0.05$).

Descriptive statistics at each visit will also be provided by surgery group for the mean UCVA for the ITT Analysis Set.

5.4 Multiplicity Strategy

In order to control the type I error at the 5% significance level ($\alpha=0.05$) over the family of primary and secondary hypotheses, the secondary effectiveness hypotheses will be relevant only if the primary effectiveness null hypothesis is rejected at the 5% significance level

(two-sided). The secondary hypotheses will then be tested using the Hochberg testing procedure.

For the secondary effectiveness endpoints, let:

- H_{0i} refers to the corresponding null hypotheses
- p_i refers to the p-values for H_{0i} , which will be calculated without any multiplicity adjustment where $i = 1, 2$ such that [1], [2] refer to the order from $p_{[1]} \leq p_{[2]}$.
- Hochberg's step-up method will proceed as follows:
 - Step 1: If $p_{[2]} < \alpha$ (where α is 0.05, two-sided), reject all H_{0i} (where $i = 1, 2$), and stop; otherwise go to Step 2.
 - Step 2: If $p_{[1]} < \alpha/2$ (where α is 0.05, two-sided), reject $H_{0[i]}$, $i = 1$, and stop.

The adjusted p-values in addition to the adjusted CIs for the secondary effectiveness endpoints will be presented.

5.5 Handling of Missing Data

The analyses of the effectiveness endpoints will be based on observed data (i.e. no imputation will be performed). The influence of missing data is expected to be minimal.

6 Safety Analysis Strategy

6.1 Safety Endpoints

The safety endpoints are:

- Mean intraocular pressure (IOP) (mmHg) at each study visit
- Mean mesopic uncorrected contrast sensitivity at each contrast level at each study visit
- Mean BCVA (logMAR) at each study visit
- Percentage of eyes with post-surgery BCVA that is ≥ 2 lines better, 1 to < 2 lines better, >0 to < 1 line better, no change, < 0 to < 1 line worse, 1 to < 2 lines worse, ≥ 2 lines worse than pre-surgery BCVA at each study visit
- Frequency of dry eye syndrome at each study visit
- Mean overall and subscale vision related quality of life score at each study visit
- Frequency of AEs

- Frequency of device deficiencies

6.2 Safety Hypotheses

There are no formal safety hypotheses in this study. The focus of the safety analysis will be a comprehensive descriptive assessment of safety endpoints listed in Section 6.1.

6.3 Statistical Methods for Safety Analyses

Except otherwise stated, the analysis set for all safety analyses is the Safety Analysis Set as defined in Section 3. It should be noted that the eye-level safety analyses will be performed using the Safety Analysis Set. For safety parameters collected on the subject-level (e.g. subject-reported outcome questionnaires, non-ocular AEs) the population of interest will be the set of subjects with at least one eye for which treatment has begun.

Baseline will be defined as the last measurement prior to surgery, except otherwise stated.

6.3.1 Adverse Events

The applicable definition of an AE is in the study protocol. All AEs occurring from when a subject signs the ICF to when a subject exits the study will be accounted for in the reporting. Analysis and presentation of AEs occurring during the 45 day pre-surgery period (the screening period) will be separated from those occurring during the post-surgery period where a comparative evaluation (descriptive only) of treatment-emergent AEs (TEAEs) is intended. A TEAE is an event not present prior to surgery (Topography Guided LASIK, SMILE) or any pre-existing event that worsens following surgery. The period for TEAE analysis starts from when study treatment has begun to 12 months post-surgery (Day 330 to Day 375). Study treatment will be considered to have begun once the flap creation is initiated for Topography Guided LASIK and once the laser touches the eye for SMILE.

Descriptive summaries (subject counts and percentages, event counts) by surgery group for specific AEs will be presented by primary SOC and PT of the Medical Dictionary for Regulatory Activities (MedDRA) dictionary (Version 19.0 or a more recent version). The SOCs will be presented in alphabetical order. PTs will be ordered for each surgery group in decreasing proportion in the Topography Guided LASIK surgery group of interest (study surgery group 1). The following summary tables will be provided:

- Ocular AEs for all eyes in the Safety Analysis Set (TEAE only)
- Ocular SAEs for all eyes in the Safety Analysis Set (TEAE only)
- Adverse device effects (ADEs) for all eyes in the Safety Analysis Set (TEAE only)

- Serious ADEs (SADEs) for all eyes in the Safety Analysis Set (TEAE only)

Both subject and event counts will be presented for AEs. Subject counts refer to the number of subjects with the respective AE of interest. Subjects who experience multiple AEs for a PT will be counted once, similarly for subjects with multiple AEs per SOC, for subject counts. Event counts refer to the number of occurrences of the respective AE of interest, regardless of whether a subject already had this event.

Individual subject's listings will also be provided. These will include:

- Ocular AEs for all eyes in the Safety Analysis Set
- Ocular AEs for all eyes not in the Safety Analysis Set
- Non-ocular AEs for all enrolled subjects
- Listing of deaths for all enrolled subjects

These listings will also include AEs that occur after signing the ICF but prior to surgery. They will comprise all events occurring during this period in any subject who consented to participate in the study with the following exception.

Although the surgery is planned to be bilateral, the investigator may decide to not perform the surgery on the second eye on the same day as the first eye. In the following scenarios, if during the 12-month post-surgery study period:

- no surgery is performed on the second eye
- surgery is performed on the second eye using non-study surgery

only AEs will be collected for this eye. These AEs (including those which are collected pre-surgery as well as those after the planned surgery) will be listed separately.

6.3.2 Best Corrected Visual Acuity

Observed values and change from baseline values for each treated eye will be presented descriptively (N, mean, median, SD, standard error [SE], minimum, and maximum) at each study visit for each surgery group.

Counts and percentages of eyes that experience pre-specified category of change from baseline to each post-surgery assessment will be presented according to the following categories: ≥ 2 lines better (≥ 0.2), 1 to < 2 lines better (0.1 to < 0.2), > 0 to < 1 line better (> 0 to < 0.1), no change (0), < 0 to < 1 line worse (> -0.1 to < 0), 1 to < 2 lines worse (-0.1 to > -0.2), ≥ 2 lines worse (≤ -0.2).

A listing will be provided which presents all subjects with ≥ 2 lines decrease (i.e. ≥ 2 lines worse) in BCVA from baseline to any visit for all randomized subjects. The listing will include the following variables: surgery group, investigator, subject, age, sex, race, ethnicity, visit, eye, baseline value, value at the visit, and a change from baseline value.

6.3.3 Biomicroscopy Findings/Slit Lamp Examination

A listing will be provided which presents all eyes with an abnormality in any slit-lamp parameter at any post-surgery visit. The listing will include the following variables: surgery group, investigator, subject, age, sex, race, ethnicity, visit, eye, parameter, baseline value and value at the visit. "Other" slit lamp examination findings will be listed along with their MedDRA dictionary (Version 19.0 or a more recent version) primary SOC and PT codes.

6.3.4 Intraocular Pressure

IOP measurements will be recorded in mmHg and rounded to the nearest whole mmHg.

Descriptive statistics (N, mean, median, SD, SE, minimum, and maximum) of observed values and change from baseline values will be presented at each study visit by surgery group.

A listing will be provided which presents all subjects with an increase or decrease in IOP of more than 10 mmHg at any visit compared to the same eye at baseline. The listing will include the following variables: surgery group, investigator, subject, age, sex, race, ethnicity, visit, eye, baseline value, value at the visit, and change from baseline value.

6.3.5 Dilated Fundus Examination

A listing will be provided which presents all eyes with an abnormality in any fundus parameter at any post-surgery visit. The listing will include the following variables: surgery group, investigator, subject, age, sex, race, ethnicity, visit, eye, baseline value, and value at the visit.

6.3.6 Mesopic Uncorrected Contrast Sensitivity

Descriptive statistics (N, mean, median, SD, SE, minimum, and maximum) of observed values in logCS (with and without glare) and change from baseline values will be presented at each study visit and contrast level (spatial frequencies of 1.5, 3.0, 6.0, 12.0, and 18.0 cd/m^2) by surgery group.

6.3.7 Subject Reported Outcomes

For RSVP, the individual items for the overall RSVP questionnaire will be categorized into 8 subscales (concern, expectations, physical/social functioning, driving, symptoms, optical problems, glare, and problems with corrective lenses), and the mean score for each subscale will be calculated. The subscale scores will then be re-scaled into a score of 0 to 100.

Descriptive statistics (N, mean, median, SD, SE, minimum, and maximum) of observed values and change from baseline values for the overall score and the eight subscale scores will be presented at each study visit by surgery group.

For SQDES, a subject is defined as having dry eye syndrome if there was occurrence of both dryness and irritation of the eyes either constantly or often (that is, severe symptoms) or a report of a previous clinical diagnosis of dry eye syndrome. A shift table showing the status of dry eye syndrome at baseline relative to each study visit will be presented by surgery group. In addition, a frequency table of SQDES status at each study visit by surgery group will be provided.

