# 8.5.2 Safety Endpoints

The secondary safety endpoints are as follows:

- Frequency of treatment-emergent AEs.
- Mean intraocular pressure (IOP) at Screening, 1 month, 3 months, and 12 months.
- Frequency of device deficiencies
- BCVA:
  - o Mean BCVA at Screening, 1 week, 1 month, 3 months, and 12 months.
  - Percentage of eyes with post-surgery BCVA more than two lines better, two lines better, one line better, less than one line better and greater than one line

Alcon - Business Use Only Protocol - Clinical Effective Date: 19-Mar-2017
Page 41 of 81

Document: TDOC-0052425 Version: 2.0; Most-Recent; Effective; CURRENT

Status: Effective

worse, one line worse, two lines worse, more than two lines worse than pre-surgery BCVA at Screening, 1 week, 1 month, 3 months, and 12 months.

- Uncorrected contrast sensitivity:
  - Mean mesopic uncorrected contrast sensitivity at each contrast level at Screening, 1 month, 3 months, and 12 months.
- Quality of vision and quality of life (for both RSVP and SQDES):
  - RSVP: Mean overall and subscale vision related quality of life score at Screening, 1 month, 3 months, and 12 months.
  - SQDES: Frequency of dry eye syndrome at Screening, 1 month, 3 months, and 12 months.

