### NOTES:

- AEs will be recorded at each visit and reported from the time of informed consent for all subjects in the study.
- Patient-reported outcomes (PROs) will be measured in the study to assess the incidence of symptoms and/or post-surgery change in symptoms from pre-surgery status via subjective ratings. These will consist of the RSVP questionnaire (Vitale 2000), a validated instrument for the measurement of vision related quality of life, and SQDES for the diagnosis of dry eye (Gulati 2006).

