### LASIK

LASIK involves the creation of a corneal flap, and the following complications may infrequently occur: decentered or dislocated flap, debris under the flap, flap tears, completely dissected flap (free flap), and flap that's too thin (Shortt 2013). These complications are managed during the surgery which may include switching to another surgical procedure such as photorefractive keratectomy (PRK).

Serious complications leading to significant permanent visual loss such as infections and corneal ectasia occur rarely with LASIK; however, complications such as chronic dry eye, starbursts, glare, halos and reduced contrast sensitivity occur more frequently (Sugar 2002). Some of these complications, such as corneal ectasia and dry eyes, may be minimized by selecting suitable subjects for LASIK. To minimize the risk of corneal ectasia, subjects with suspicious pre-surgery topographies and thin corneas should not be treated with LASIK. To minimize the risk of chronic dry eye, existing dry eye should be treated prior to the LASIK. It is more challenging to minimize the visual symptoms risks such as glare, halos, starbursts, and reduced contrast sensitivity because these complications are inherent to how refractive surgery works. Subject education of the possibility of having these types of complications is key.

The risks of Topography Guided LASIK are not known to be different than the risks of other methods of LASIK.

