### 10.2 Exclusion Criteria

Below is a list of exclusion criteria. Ocular criteria must not be met in either eye.

- 1. Pregnancy or lactation, current or planned, during the course of the study.
- 2. Manifest refraction astigmatism that is more than 1.00 D than the topolyzer astigmatism assessed by Contoura software.
- Mixed astigmatism refractive error.
- 4. Degenerations of structure of the cornea including diagnosed keratoconus, forme fruste kerataconus or pellucid marginal degeneration.
- 5. Dry eye as identified by the SQDES.
- 6. A calculated residual stromal bed thickness that is less than 250  $\mu$ m.
- 7. History or evidence of active or inactive corneal or other anterior segment disease (e.g, herpes simplex keratitis, recurrent erosion syndrome).
- 8. Diagnosed advanced glaucoma.
- 9. Uncontrolled diabetes.

Print Date:

Alcon - Business Use Only Protocol - Clinical Effective Date: 19-Mar-2017 Page 48 of 81

Document: TDOC-0052425 Version: 2.0; Most-Recent; Effective; CURRENT

Status: Effective

10. Nystagmus or any other condition that would prevent a steady gaze during the treatment.

- 11. Previous intraocular or corneal surgery.
- 12. Weakened immune system, including diagnosed collagen vascular, autoimmune or immunodeficiency disease.
- 13. Systemic medications that may affect corneal healing including, but not limited to steroids, antimetabolites, immune response modifying drugs, etc.
- 14. Presence or history of any condition or finding that makes the subject unsuitable as a candidate for refractive surgery or study participation or may confound the outcome of the study, in the opinion of the Investigator.
- 15. Any subject currently participating in another investigational drug or device study that may confound the results of this investigation.
- 16. A known sensitivity to medications used during the study.

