## 12.1.1 Pre-Surgery screening Visit (Day -45 to Day -1)

Below is a list of study procedures to be undertaken at Pre-Surgery Visit (Screening). The procedures must be performed in the order presented below unless otherwise stated. All ocular assessments must be done monocularly.

For applicable assessments, both eyes must qualify for the study, therefore the screening assessments will be performed in both eyes.

Upon signing the informed consent, subjects are considered enrolled. The subject is assigned a single subject identifier at the Pre-Surgery Visit. The subject identifier consists of a combination of a 4 digit investigator number and a 5 digit subject number. The number is automatically generated sequentially by the EDC system. As an example: "4584.00001" (The investigator number and subject number are separated by a "." character).

This number is used throughout the clinical study. Within 45 business days of surgery, subjects will be screened and randomized based on 1:1 allocation to receive EX500 for Topography Guided LASIK or VisuMax for SMILE.

1. Upon identification of a possible study participant, carry out the informed consent process. Refer to Section 16.2 Informed Consent Procedures.

*NOTE*: Subjects must formally consent to participate in the study prior to undergoing any study specific testing. Upon signing informed consent, subjects are considered enrolled in

Alcon - Business Use Only Protocol - Clinical Effective Date: 19-Mar-2017
Page 54 of 81

Document: TDOC-0052425 Version: 2.0; Most-Recent; Effective; CURRENT

Status: Effective

the study.

2. Perform a urine pregnancy test if the subject is a woman of childbearing potential.

- 3. Document demographics, ocular and non-ocular medical history, ocular and non-ocular concomitant medications.
- 4. Administer the RSVP Questionnaire (a 52-item questionnaire) to assess quality of vision and vision related quality of life.
- 5. Administer the SQDES to evaluate dry eye symptom and severity.

*NOTE:* Investigators and site staff must review both questionnaires results prior to subjects leaving the office to ensure completeness.

6. Conduct the following procedures in an order that is feasible for your site:

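### The dry-eye shift table in SAP 6.3.7 has an empty baseline 'yes' row by design and repeats the frequency table, while no by-arm summary of the dryness and irritation ratings is planned

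*SAP*

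**What the plan says.** **Entry.** Protocol 10.2, criterion 5, excludes "Dry eye as identified by the SQDES". Section 10.2 gives no scoring rule. The only one in the documents is in Protocol 15.7 and SAP 6.3.7: "a subject is defined as having dry eye syndrome if there was occurrence of both dryness and irritation of the eyes either constantly or often", or else a "report of a previous clinical diagnosis of dry eye syndrome".

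**Timing.** Protocol Table 6-1 schedules the SQDES at Screening and Months 1, 3 and 12. SAP 2.3 takes the last non-missing value before surgery as baseline.

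**Endpoint.** Protocol 8.5.2 lists "SQDES: Frequency of dry eye syndrome at Screening, 1 month, 3 months, and 12 months".

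**Planned outputs.** SAP 6.3.7 plans two tables, both of the yes/no status. The first: "A shift table showing the status of dry eye syndrome at baseline relative to each study visit will be presented by surgery group". The second is a frequency table of status at each visit by surgery group.

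**Stated purpose.** Protocol 12.1.1, step 5, reads: "Administer the SQDES to evaluate dry eye symptom and severity". The notes to Protocol 9.2.1 say the patient-reported outcomes are there "to assess the incidence of symptoms and/or post-surgery change in symptoms from pre-surgery status via subjective ratings".

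**Risk.** Protocol 9.3.1, on LASIK, says that "complications such as chronic dry eye, starbursts, glare, halos and reduced contrast sensitivity occur more frequently".

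**The concern.** The status that decides entry is the same status that is cross-tabulated at baseline. A shift table is useful when subjects start in different states. Here, apart from deviations, they all start in one.

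The yes/no status is also coarse. On symptoms it needs both dryness and irritation at a high frequency. A subject who goes from no dryness to constant dryness, with only occasional irritation and no clinical diagnosis, is 'no' at baseline and 'no' afterwards. Because entry removes subjects at or above the threshold, much of the information after surgery lies in movement below it, and neither table can show that movement.

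The stake is how well dry eye is described for each arm. The Protocol names chronic dry eye among the more frequent LASIK complications, and LASIK is the test procedure. With only the two planned tables, a by-arm difference in one symptom could be understated.

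**Working it through.** The documents give no figure for SQDES, so there is no planned number to reproduce. The sample size (185 subjects per arm) concerns the primary endpoint and plays no part here.

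**1. Is the baseline 'yes' row empty?**

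- Exclusion 5 bars SQDES-positive subjects. This step assumes it uses the rule in Protocol 15.7 and SAP 6.3.7.
- The only scheduled SQDES before surgery is at Screening, so that answer is normally the baseline.
- A repeat before surgery does not refill the row. Protocol 9.2.1 and 12.1.2 require the criteria to be reviewed again before surgery and a subject who no longer qualifies to be discontinued.
- SAP 3 admits to the Safety Analysis Set only eyes for which treatment has begun, and for subject-level data a subject needs at least one such eye.

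Baseline 'yes' in the analysed population is therefore 0, apart from treated subjects with an eligibility deviation.

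**2. What is left of the table?** At each visit the status shift table has 2 × 2 = 4 cells. With the 'yes' row at 0, two remain: 'no' to 'no' and 'no' to 'yes'. Take the 200 treated subjects per arm expected in Protocol 15.9, assume all have baseline and visit data, and assume a range of positive rates after surgery (not from the documents):

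| Assumed positive rate | 'No' to 'yes' | 'No' to 'no' | From baseline 'yes' | Positive in frequency table |
|---|---|---|---|---|
| 2% | 4 | 196 | 0 | 4 |
| 5% | 10 | 190 | 0 | 10 |
| 10% | 20 | 180 | 0 | 20 |
| 20% | 40 | 160 | 0 | 40 |
| 30% | 60 | 140 | 0 | 60 |

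The second and last columns agree at every rate, so the shift table adds nothing to the frequency table. It still shows new onset at the threshold.

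**3. How much could the threshold hide?** Assume, for illustration only, that dryness is often or constant in 30% with LASIK and 15% with SMILE, a difference of 15 points. Leave the diagnosis route aside. The difference in 'both symptoms' then depends on irritation:

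- Irritation 10% in each arm, all irritated subjects also dry: min(30%, 10%) = 10% against min(15%, 10%) = 10%, difference 0.
- Irritation 10% in each arm, independent of dryness: 0.30 × 0.10 = 3.0% against 0.15 × 0.10 = 1.5%, difference 1.5 points.
- Irritation always accompanying dryness (30% and 15%): 30% against 15%, difference 15 points.

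These are scenarios, not bounds. The documents give no rates that would favour one of them.

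**4. Is there another by-arm summary of the ratings?** SAP 6.3.7 names none. In the same section the RSVP gets change from baseline for its overall score and all eight subscales.

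**The case against.** The strongest reply is that the SAP delivers what the Protocol asks for. The endpoint in Protocol 8.5.2 is the frequency of dry eye syndrome, Protocol 15.7 defines it as a yes/no status, and the notes to Protocol 9.2.1 describe the SQDES as a diagnostic tool. The purpose sentence there is worded as incidence and/or change, so a change analysis is one of two options. All of this stands. The Protocol does not require a graded table, and a redundant table is not an error.

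Other outputs also bear on dry eye:

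- SAP 2 lists all data by default, so individual ratings can be read.
- Protocol 13.2 has clinically relevant worsening of a questionnaire response reported as an AE, and SAP 6.3.1 tabulates ocular treatment-emergent AEs by arm.
- A diagnosis during follow-up can turn a subject 'yes' without the two-symptom rule.
- The RSVP has a symptoms subscale.

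These soften the point without removing it. A listing does not compare arms. The AE route depends on the investigator's view of clinical relevance, and under SAP 1.4 staff giving the questionnaires may know the assignment. The documents do not say that the RSVP subscale measures dryness.

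Three stronger readings are tempting and not supported:

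- A reader might infer that the shift table shows no change at all. It shows new onset at the threshold, and it would separate any eligibility deviation from a new case.
- A reader might infer that the ratings go unused. They determine the status and are listed. What is missing is a summary by arm.
- A reader might take the Protocol to say that dry eye is more frequent with LASIK than with SMILE. The sentence in 9.3.1 contrasts frequent with rare complications of LASIK, and the SMILE part of that section lists dry surface among its own complications.

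**Conclusion.** The point holds as a reporting weakness. By design, half the cells of the status shift table are empty apart from deviations, and the rest essentially repeat the frequency table. The plan has no by-arm summary that can show dryness or irritation worsening below the threshold, although the questionnaire is given to evaluate symptom and severity.

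This rests on two assumptions: that exclusion 5 uses the only SQDES rule the documents give, and that eligibility deviations are few. The size of any masked difference cannot be derived. The scenarios run from 0 to the full 15 points shown, depending on how irritation tracks dryness.

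The safety analyses are descriptive, so type I error, power and the primary conclusion are not affected. The change is worth making because it is cheap and uses data already collected.

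**What to change.** In SAP 6.3.7:

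1. Keep the frequency table of SQDES status by visit and surgery group, which is the Protocol endpoint. Add a footnote giving any treated subjects who were positive at baseline.
2. Replace the status shift table with two descriptive shift tables, one for the dryness rating and one for the irritation rating, from Screening baseline to Months 1, 3 and 12 by surgery group. Use the response categories recorded on the questionnaire, since the Protocol and SAP do not print the full scale.
3. Under each table, give the number and percentage of subjects whose rating moved to a more frequent category than at baseline.

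**Cost.** A wording change to the SAP before database lock, one table replaced by two, and a few more descriptive cells. No new data, no testing and no change to any endpoint.
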